#### **2.4 Advantages of the SPR System over alternative Surface Electrical Stimulation therapies**

The SPR System has significant advantages over alternative Surface Electrical Stimulation therapies.

*Consistent targeted stimulation.*

The SPR System leads are placed and anchored [REDACTED], ensuring consistent stimulation [REDACTED] across treatment sessions, leading to greater reliability of the therapy. Consistent stimulation of the motor points ensures neurostimulation therapy is delivered to the affected area. Consistency is not ensured with surface stimulation, as electrodes must be placed for each therapy session, and could be placed in varying locations each time.

***Reduced patient and clinician training.***

Leads are placed only once by skilled personnel during the initial lead placement. Skilled personnel and intense patient training are not needed to ensure proper placement of leads for each subsequent treatment session, as is the case with the placement of surface electrodes.

***Reduced stimulation-induced pain.***

[figure not shown]
[REDACTED] electrical stimulation is less painful and better tolerated than surface electrical stimulation (Yu, et al., 2001). It is critical to the success of the therapy and overall patient compliance to be able to deliver the stimulation therapy in a comfortable and tolerable way.

***Reduced [REDACTED] fatigue.***

[REDACTED] electrical stimulation can be delivered at a lower stimulation frequency, which is associated with reduced muscle fatigue. Higher stimulation frequencies are used with surface electrical stimulation systems to minimize stimulation-induced cutaneous pain. It is important to minimize the potential for muscle fatigue in post-stroke patients so that they can still participate in the rehabilitation therapies for motor recovery.

***Long-term pain relief.***

The SPR Implant Stage uses the implantable SPR System, which enables patients to treat their pain symptoms if and when they return. This offers a long-term solution to shoulder pain that is within the patient's control. In addition, some individuals may have long-term pain relief following the short-term Smartpatch therapy.

[REDACTED]

[REDACTED]

## 2.6 Summary

[REDACTED]

The results obtained thus far suggest that [REDACTED] stimulation has the potential to be a safe and effective treatment option for post-stroke shoulder pain, but an approach using fewer leads and the option for a fully implantable system is needed to ensure ease of implementation and long-term effectiveness. The pilot study will be conducted by the sponsor, SPR Therapeutics, to gather preliminary safety, efficacy, and technical performance data on the SPR System. [REDACTED]

[REDACTED]

## 3.0 INVESTIGATIONAL DEVICE DESCRIPTION

### 3.1 Overview

The SPR System is a 2-stage neurostimulation device that applies electrical stimulation therapy [REDACTED] for the treatment of post-stroke shoulder pain. In the first stage (the SPR Trial Stage), [REDACTED]

[REDACTED] Trial stimulation is delivered for three weeks (following a 3-week off period for evaluation of sham stimulation) using an external stimulator (the Smartpatch Stimulator). If clinically meaningful pain reduction is achieved (at least a 2-point reduction on the Brief Pain Inventory Short Form Question #3) during the SPR Trial Stage but pain returns within 6 months and is sustained for two consecutive weeks, the subject progresses to receive an Implantable Pulse Generator (IPG) and Implantable [REDACTED] lead for long-term therapy (the SPR Implant Stage).

The SPR System consists of a Trial System and an Implant System, which are described in further detail below.

#### 3.1.1 SPR Trial System (i.e., Smartpatch System) Components

The SPR Trial System consists of a:

- Percutaneous [REDACTED] Lead and Introducer (called the Smartpatch Lead and Introducer);
- A miniature programmable body-worn external stimulator and associated components known as the Smartpatch PNS System (comprised of a Smartpatch Stimulator, Smartpatch Pad, Smartpatch Cable supplied in two lengths, Smartpatch Test Cable, Smartpatch Test Needles, Smartpatch Lead Connector, Smartpatch Lead Connector Tape, and bandages).
- The Checkpoint® Test Stimulator and Test Cable (not shown in Figure 2) may be used by the Clinician to place the Lead

[figure not shown]
Figure 2. SPR Trial System

3.1.1.1 Smartpatch Lead [REDACTED]

3.1.1.2 Smartpatch Lead Connector, Torque Wrench, and Lead Connector Tapes [REDACTED]

3.1.1.3 Smartpatch Stimulator [REDACTED] and Smartpatch Pad ([REDACTED])

[REDACTED]

[figure not shown]
[REDACTED]

[REDACTED]

[REDACTED]

#### 3.1.1.4 Smartpatch Cable [REDACTED]

[figure not shown]
[figure not shown]

**3.1.1.5 Checkpoint® Test Stimulator [REDACTED] and Checkpoint Test Cable**

[figure not shown]

**3.1.1.6 Smartpatch Test Cable**

**3.1.1.7 Smartpatch Test Needle**

**3.1.1.8      Accessories**

**3.1.2    SPR Implant System Components**

3.1.2.1    **Implantable Pulse Generator (IPG)**

[REDACTED]

[REDACTED]

[REDACTED]

### **3.1.2.2 Implantable Lead**

SPR Therapeutics, LLC.  
0122-CSP-001-P  
102

**CONFIDENTIAL**

Clinical Programmer

A large, solid black rectangular box with a thin blue border, positioned below the first redaction. It covers the majority of the page content, suggesting a redaction of a long document or list.

[REDACTED] IPG Remote [REDACTED], Charger [REDACTED] and IPG Shut-Off  
Magnet [REDACTED]

*IPG Remote*

[figure not shown]

*IPG Charger*

[figure not shown]
*IPG Shut-off Magnet*

Checkpoint Test Stimulator

Modified IPG Remote

## 4.0 STUDY DESIGN

### 4.1 Overview

This study is a prospective non-randomized multicenter case series pilot study to gather preliminary data on the safety, clinical efficacy, and performance of the SPR System for the treatment of post-stroke shoulder pain.

Subjects with chronic ( $\geq 6$  months) post-stroke shoulder pain rated as  $\geq 4$  on the Brief Pain Inventory pain intensity question #3 (BPI3) will receive the first stage of the SPR System. The SPR System is a two-staged neurostimulation therapy which delivers stimulation [REDACTED]. The first stage (SPR Trial Stage) uses a temporary [REDACTED] lead placed percutaneously in [REDACTED] and connected to a body-worn external stimulator (the Smartpatch Stimulator). Subjects meeting the specified success criteria at the conclusion of the SPR Trial Stage who then experience a return of pain within 6 months that is sustained for two consecutive weeks will be consented and screened for eligibility for the second stage (SPR Implant Stage). A “return of pain” is defined as: 1) an increase in pain by at least 2 points compared to the end

of Trial Stage (Visit 5) pain score; and 2) BPI Question #3 score of at least 4 (both criteria must be met for at least 2 weeks). The SPR Implant Stage uses an Implantable Pulse Generator (IPG) and Implantable [REDACTED] Lead.

Subjects will be permitted to continue use of non-opioid analgesic medications throughout the study; however, dosages of these medications will be controlled during the study. Subjects will be permitted to reduce or maintain their dosage of non-opioid analgesic medications, however, they will be asked to not increase their dosage of these medications above their baseline dosage during the week prior to each study visit and scheduled telephone call (and during the Trial Stage follow-up period). Subjects will not be permitted to use opioid analgesic medications (except in the week immediately following the implant stage surgery as needed to control post-surgical pain), or other treatment methods, including slings or other stabilization devices/methods, Botox or steroid injections to the affected shoulder area, etc, during study participation. For this study, Tramadol (Ultram, Ultram ER, or Ultracet) will be considered an opioid medication, and thus, not permitted during study participation. Subjects who require concurrent physical or occupational therapy for shoulder pain will be excluded.

Subjects will use the Smartpatch System for 6-weeks during the Trial Stage. To evaluate the placebo effect, the first 3-weeks of the SPR Trial Stage consist of a sham period in which the SPR Trial Stage device (i.e., the Smartpatch System) is placed, but stimulation is not delivered. Subjects are told that stimulation during lead placement may feel different than stimulation therapy. [REDACTED]

[REDACTED] Subjects will be blinded to the fact that stimulation is not being delivered. Following the sham period, stimulation will be delivered, and subjects will receive stimulation for a total of 6 hours each day for 3 weeks. Subjects will be queried for pain intensity on a weekly basis during the SPR Trial Stage using the BPI Short Form Question #3 (BPI3), and subjects will be instructed to focus on their shoulder pain when answering the BPI. Pain intensity at the end of the sham period will be compared to baseline pain intensity score to evaluate the placebo effect. At the conclusion of the SPR Trial Stage, subjects achieving at least a 2-point reduction on the BPI3 will receive monthly follow-up calls for up to six months in order to determine eligibility to advance to the SPR Implant Stage. During the Implant Stage, subjects will receive the fully implantable SPR Implant Stage system and be followed for three years.

All primary and secondary endpoints will be assessed at baseline and again at the completion of the sham period and the SPR Trial Stage. In addition, primary endpoints will be evaluated at all phone calls during the Trials Stage follow-up period and at all follow-up intervals during the SPR Implant Stage (3-weeks, 6-weeks, 12-weeks, 6-months, 9-months, and 12-months post IPG Stim ON). In addition, long-term follow-up will be conducted on an annual basis at 24-Months and 36-Months IPG Stim On.

Primary efficacy of the Trial Stage therapy will be determined at the end of the Trial Stage. Primary efficacy of the Implant Stage will be determined at the 12-week post-IPG Stim On follow-up visit. A subject will be considered a Trial Stage Success if he/she achieves at least a 2-point reduction in post-stroke shoulder pain intensity score in the BPI Pain Intensity Question #3 (BPI3) at the end of the Trial Stage (Visit 5) relative to end of the placebo period or baseline (Visit 4 or Visit 1), whichever is lower OR reports a BPI3 score of zero at the end of the Trial Stage.

A subject will be considered an Implant Stage success if he/she achieves at least a 2-point reduction in post-stroke shoulder pain intensity score in the BPI Pain Intensity Question #3 (BPI3) at the 12-week post-IPG stim on visit (Visit 10) relative to end of the placebo period or baseline (Visit 4 or Visit 1), whichever is lower OR reports a BPI3 score of zero at the 12-week post-IPG stim on visit.

All Implant Stage subjects will continue to be evaluated through the 36-month IPG Stim ON follow-up interval to determine the safety profile of the SPR Implant System and to evaluate the effect of dosage on treatment effect. Adverse events will be assessed at all follow-up visits.

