
	
Implant Stage, subjects will receive the fully implantable SPR Implant Stage system and be followed for 3 years.
 
All primary and secondary endpoints will be assessed at baseline and again at the completion of the sham period and the active stimulation period of the SPR Trial Stage. In addition, primary endpoints will be evaluated via monthly phone calls during the Trial Stage follow-up period as well as at visits during the SPR Implant Stage (3-weeks, 6-weeks, 12-weeks, 6-months, 9-months, and 12-months post IPG Stim ON). In addition, long-term follow-up will be conducted on an annual basis at 24-months and 36-months post IPG Stim ON.
 
Primary efficacy of the Trial Stage will be determined at the end of the Trial Stage. Primary efficacy of the Implant Stage will be determined at 12-weeks post IPG Stim ON. All Implant Stage subjects will continue to be evaluated at 6, 9, and 12-months post IPG Stim ON follow-up visits and annually for 36 months to determine the long-term efficacy and safety profile of the SPR Implant System and to evaluate the effect of dosage (number of hours of use each day) on treatment effect. Adverse events will be assessed at all follow-up visits.

Number of Sites	Up to 5 Investigational Sites will be enrolled
Number of Subjects	45 subjects will participate in the SPR Trial Stage. Although we expect to yield approximately 18 subjects with an implantable system (SPR Implant Stage), all eligible Implant Stage subjects will be permitted to advance to the Implant Stage.

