#### **4.2.2.1     Subject Disposition following infection of Percutaneous or Implantable Leads**

Subjects with infections related to the implanted electrodes will be treated and dispositioned according to the severity of the infection and the SPR stage (Trial or Implant). In the Trial Stage, subjects who develop a mild infection will receive the appropriate medical treatment (such as administration of antibiotics or wound cleansing) and the Smartpatch Lead will remain in the shoulder. An infection is considered to be “mild” when: 1) it is a superficial infection that does not involve a fever 2) it can be treated with topical antibiotics and/or appropriate cleansing agents and 3) it does not place the subject at risk for a deep tissue infection. These subjects will continue in the study.

Subjects who develop a moderate or severe infection (i.e any infection beyond what is described as mild above) during the Trial Stage or any infection of the components (Implantable Lead or IPG) during the Implant Stage will have the SPR System removed. These subjects will be followed until resolution of the infection. Upon resolution, the subject will be terminated from the study.

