#### **4.5.3.14 Explant Follow-Up Visit**

Subjects requiring an explant of the SPR Implant Stage System (either the IPG, Implantable IM Lead, or both) will be required to return to the clinic for a 1-week follow-up visit after the explant procedure.

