#### **4.5.3.15 Revision Surgery Visit(s) -If Applicable**

As noted in the risk section of this protocol, it is possible that subjects may require a revision surgery due to 1) migration of the implantable components resulting in loss of efficacy or subject discomfort, 2) failure of the implantable components, 3) rejection of the implantable components, 4) removal of the system due to a medical condition that requires MRI scanning, or 5) any other medical condition which necessitates removal of the system. If a revision surgery is necessary, the risks and any potential benefits of undergoing an additional surgical procedure will be discussed with the subject. Revision surgeries carry the same risks as the original implantation procedure and any additional subject specific risks will be discussed with the subject prior to any revision surgery. Additional visits to the clinic will also be necessary if a revision procedure is performed.

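### The plan promises 36-month safety follow-up for every implanted subject, but terminates those with a component infection once it resolves and does not say what follows the 1-week visit after explant

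*Combined protocol and SAP*

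**What the plan says.** Three parts of the protocol bear on how long an implanted subject is observed.

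- **The general promise.** Section 4.1: "All Implant Stage subjects will continue to be evaluated through the 36-month IPG Stim ON follow-up interval to determine the safety profile". The Synopsis (Study Plan) says that "subjects will receive the fully implantable SPR Implant Stage system and be followed for 3 years", and Section 4.1 repeats the three-year period.
- **The infection rule.** Section 4.2.2.1 provides that subjects with "any infection of the components (Implantable Lead or IPG) during the Implant Stage will have the SPR System removed". It continues: "These subjects will be followed until resolution of the infection. Upon resolution, the subject will be terminated from the study".
- **The explant visit.** Section 4.5.3.14 covers removal of the pulse generator, the lead or both, and says that these subjects "will be required to return to the clinic for a 1-week follow-up visit after the explant procedure". It does not mention later visits. Section 4.5.3.15, on revision surgery, adds that "Additional visits to the clinic will also be necessary if a revision procedure is performed", without giving their number or duration.

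The primary safety endpoint is the occurrence and type of device-related adverse events (Synopsis; Section 4.4.1.2). About 18 subjects are expected to receive an implant (Synopsis; Table 3).

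**The concern.** The promise in Section 4.1 covers all implanted subjects, yet Section 4.2.2.1 takes out a group defined by a device-related event. A component infection is the kind of outcome that the primary safety endpoint counts, and it is also what ends observation. Follow-up beyond that point therefore comes disproportionately from subjects who kept the device without such trouble. A late consequence of infection or removal, or a new event, could occur in a terminated subject with no scheduled contact to detect it.

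For explants not caused by infection, the difficulty is silence. Sites could reasonably differ: one might keep the subject on the visit schedule, another might close the record after the 1-week visit. Table 4 has no disposition category for explanted subjects that would settle it.

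This matters because the pilot is meant to inform a larger pivotal study (Section 1.5) and to refine consent forms and the risk-benefit profile (Section 5.4.2). With about 18 implants, each subject is 1/18 = 5.6% of the cohort.

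**Working it through.** The plan states no figure on this point, so there is none to reproduce. The check is a comparison of text, followed by an illustration of size.

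**Step 1. Can the statements both hold?** Section 4.1 and the Synopsis: all Implant Stage subjects, through 36 months. Section 4.2.2.1: any Implant Stage component infection leads to removal, follow-up to resolution, then termination. A subject whose infection resolves before month 36 cannot satisfy both. This is a stated rule in conflict with a stated promise, and no redaction touches either sentence.

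**Step 2. Do other provisions fill the gap?**

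- Section 4.4.1.2 documents adverse events that occur during the study. An event that begins after termination falls outside that scope.
- Section 7.4 follows adverse events to resolution. This covers events already known and does not look for new ones.
- Section 6.1.2.4 keeps subjects whose system was removed for an adverse event in the success analysis. That is an efficacy provision.
- Section 6.2 bases the final analysis on the 36-month visit, which a terminated subject will not have.

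None of these detects a new event after termination.

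**Step 3. Explant without infection.** Section 4.5.3.14 sets a minimum of one visit at one week and neither ends nor continues the schedule. It also applies where only one component is removed, so some of these subjects still carry hardware.

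**Step 4. Size, as an illustration.** Inputs: n = 18 implanted and 36 months of follow-up (Synopsis). Assumptions, because the documents give no infection or explant rate: k = 1 to 3 subjects leave, at month m between 3 and 12.

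Planned follow-up: 18 × 3 = 54 person-years. Follow-up lost: k(36 − m)/12.

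- Smallest loss: k = 1, m = 12 gives 1 × 24/12 = 2.0 person-years, and 2.0/54 = 3.7%.
- Largest loss: k = 3, m = 3 gives 3 × 33/12 = 8.25 person-years, and 8.25/54 = 15.3%.

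If no late event is seen among n subjects, the one-sided 95% upper bound for its probability is 1 − 0.05^(1/n):

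| Subjects followed | Upper bound |
|---|---|
| 18 | 15.3% |
| 17 | 16.2% |
| 16 | 17.1% |
| 15 | 18.1% |

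(The two values of 15.3%, one for person-years and one for the bound at n = 18, agree by coincidence.) The bound assumes that the subjects still followed are representative of all those implanted. Exit triggered by a device-related event undermines that assumption, and the bound does not measure the consequence.

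**The case against.** The strongest reply is that the harm itself is not lost, and this is correct. The infection or removal event is documented with severity, device relationship, treatment and resolution (Sections 4.4.1.2 and 5.4.2), followed to resolution (Sections 4.2.2.1 and 7.4), and reviewed at least annually (Section 6.1.1). Removals for an adverse event remain in the success analysis (Section 6.1.2.4). A reader might infer that subjects harmed by the device drop out of the long-term safety data. The documents do not support that: only observation after resolution is lost, and subjects with device-related events that lead to neither infection termination nor explant stay on schedule.

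A reader might also infer that explanted subjects get a 1-week visit and nothing more. Section 4.5.3.14 does not say so. Where the protocol means exit it says so, as in Sections 4.2.2.1, 4.5.2.9 and 4.5.2.10, and for explants without infection the general promise in Section 4.1 can still govern. The explant provision is therefore a gap, not a stated exit.

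A third tempting inference is that retained lead fragments, listed among the Implant Stage risks in Section 8.2.2, will go unobserved. The text under those risks is redacted and may describe monitoring. A fragment problem recorded as an adverse event would in any case be followed to resolution under Section 7.4.

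Nor do the documents establish any number of removals, or that those removed are at highest later risk. Some risks need hardware in place and end with complete removal. One exit moves the bound only from 15.3% to 16.2%, which is small beside the imprecision of 18 subjects.

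It can fairly be added that this is a preliminary case series, and that pain scores collected after complete explant would not describe the device in use. What remains is the conflict in Step 1 and the finding in Step 2 that no provision looks for new events after termination.

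**Conclusion.** The concern holds in a limited form. The promise of 36-month evaluation for all implanted subjects contradicts the termination rule for Implant Stage infections, and the plan leaves follow-up after other explants unstated. The loss is confined to new or late events after resolution, or after the 1-week explant visit if a site stops there. It is selective because a device-related event is what ends observation in the infection case.

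Its numerical size is modest: assuming 1 to 3 exits from about 18 implants, the zero-event bound rises by 0.9 to 2.8 percentage points (16.2 − 15.3 and 18.1 − 15.3). The number of exits is an assumption that the documents can neither confirm nor refute. The case for acting rests on the contradiction and on the selective nature of the exit, not on lost precision.

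**What to change.** Reconcile Section 4.1 and the Synopsis with Sections 4.2.2.1 and 4.5.3.14:

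1. State that every subject who received an implant, and who does not withdraw consent, stays in adverse-event follow-up at the remaining scheduled time points to 36 months after an infection resolves or a component is explanted. Telephone contact is enough; the protocol already asks about adverse events by telephone (Sections 4.5.2.10, 4.5.3.4 and 4.5.3.5).
2. State that safety is summarised on all implanted subjects, with events after explant shown separately.
3. Treat BPI3 after explant as optional.

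This changes study follow-up only and leaves the device removal rule as it stands.

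The cost is a few telephone contacts and amendment and consent wording. A subject leaving just after the 12-week visit has five scheduled time points left (6, 9, 12, 24 and 36 months); one leaving after the 12-month visit has two. Under the same assumption of 1 to 3 exits, that is between 1 × 2 = 2 and 3 × 5 = 15 calls over the whole study. The downside is a small added burden on those subjects.
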